12.2 Reporting of adverse events

All events meeting the definition of an AE must be collected and reported. This includes events from the first trial-related activity after the patient has signed the informed consent until the end of the post-treatment follow-up period (visit 17). The events must be recorded in the applicable eCRF forms in a timely manner, see timelines below and [Figure 12-1](#)

During each contact with the trial site staff, the patient must be asked about AEs and technical complaints, for example by asking: “Have you experienced any problems since the last contact?”

All AEs, either observed by the investigator or patient, must be reported by the investigator and evaluated. All AEs must be recorded by the investigator on an AE form. The investigator should report the diagnosis, if available. If no diagnosis is available, the investigator should record each sign and symptom as individual AEs using separate AE forms.

For SAEs, a safety information form must be completed in addition to the AE form. If several symptoms or diagnoses occur as part of the same clinical picture, one safety information form can be used to describe all the SAEs.

AESIs regardless of the seriousness, must be reported using the AE form and safety information form

Protocol
 Trial ID: NN7415-4255
 UTN: U1111-1179-3872
 EudraCT no.: 2016-000614-29

~~CONFIDENTIAL~~

Date: 05 May 2017 | **Novo Nordisk**
 Version: 2
 Status: Final
 Page: 87 of 124

For all non-serious AEs, the applicable forms should be signed when the event is resolved or at the end of the trial at the latest.

Timelines for initial reporting of AEs:

The investigator must complete the following forms in the case report form (CRF)/eCRF within the specified timelines:

- **SAEs:** The AE form **within 24 hours** and the safety information form **within 5 calendar days** of the investigator's first knowledge of the SAE.

[figure not shown]
Both forms must be signed within 7 calendar days from the date the information was entered in the eCRF.

For SAEs requiring reporting on a specific event form: In addition to the above the specific event form within **14 calendar days** from the investigator's first knowledge of the AE.

- **Non-serious AEs fulfilling the AESI criteria:** The AE form and safety information form **within 14 calendar days** of the investigator's first knowledge of the event.

If the eCRF is unavailable, the concerned AE information must be reported on a paper AE form and sent to Novo Nordisk by fax, e-mail or courier within the same timelines as stated above. When the eCRF becomes available again, the investigator must enter the information on the form into the eCRF.

Contact details (fax, telephone, e-mail and address) are provided in the investigator trial master file.

Timelines are for the completion of forms from the time of investigator's awareness
 AEs requiring specific event forms are described in Section 12.1.5 and 12.1.6

AE: Adverse event **AESI:** Adverse event of special interest **SIF:** Safety information form

Protocol
 Trial ID:NN7415-4255
 UTN:U1111-1179-3872
 EudraCT no.:2016-000614-29

~~CONFIDENTIAL~~

Date: 05 May 2017
 Version: 2
 Status: Final
 Page: 88 of 124

Novo Nordisk

Figure 12–1 Reporting of AEs

Novo Nordisk assessment of AE expectedness:

Novo Nordisk assessment of expectedness is performed according to the following reference documents: Investigator’s Brochure; Current version and any updates thereto.

Reporting of trial product-related SUSARs by Novo Nordisk:

Novo Nordisk will notify the investigator of trial product-related suspected unexpected serious adverse reactions (SUSARs) in accordance with local requirements and ICH GCP¹. In addition, the investigator will be informed of any trial-related SAEs that may warrant a change in any trial procedure.

In accordance with regulatory requirements, Novo Nordisk will inform the regulatory authorities, including EMA, of trial product-related SUSARs. In addition, Novo Nordisk will inform the International Review Boards/Independent Ethics Committees (IRBs/IECs) of trial product-related SUSARs in accordance with local requirement and ICH GCP¹, unless locally this is an obligation of the investigator.

Novo Nordisk products used as concomitant medication or non-investigational medicinal product:

If an AE is considered to have a causal relationship with a Novo Nordisk marketed product used as non-investigational medicinal product rFVIII (turoctocog alfa) *or* concomitant medication in the trial, it is important that the suspected relationship is reported to Novo Nordisk, e.g. in the alternative aetiology section on the safety information form. Novo Nordisk may need to report this adverse event to relevant regulatory authorities.

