12.1.2 Serious adverse event

A serious adverse event (SAE) is an experience that at any dose results in any of the following:

- Death.
- A life-threatening^a experience.
- In-patient hospitalisation^b or prolongation of existing hospitalisation.
- A persistent or significant disability or incapacity^c.
- A congenital anomaly or birth defect.
- Important medical events that may not result in death, be life threatening^a or require hospitalisation^b may be considered an SAE when - based on appropriate medical judgement - they may jeopardise the patient and may require medical or surgical intervention to prevent one of the outcomes listed in the definition of SAE^d.

^a. The term “life threatening” in the definition of SAE refers to an event in which the patient was at risk of death at the time of the event. It does not refer to an event which hypothetically might have caused death if it was more severe.

^b. The term “hospitalisation” is used when a patient:

- Is admitted to a hospital or in-patient, irrespective of the duration of physical stay, or
- Stays at the hospital for treatment or observation for more than 24 hours

Protocol
 Trial ID:NN7415-4255
 UTN:U1111-1179-3872
 EudraCT no.:2016-000614-29

~~CONFIDENTIAL~~

Date:	05 May 2017	Novo Nordisk
Version:	2	
Status:	Final	
Page:	80 of 124	

Medical judgement must always be exercised, and when in doubt, the hospital contact should be regarded as a hospitalisation. Hospitalisations for administrative, trial related and social purposes do not constitute AEs and should therefore not be reported as AEs or SAEs. Hospital admissions for surgical procedures, planned before trial inclusion, are not considered AEs or SAEs.

^cA substantial disruption of a patient's ability to conduct normal life functions (e.g. following the event or clinical investigation the patient has significant, persistent or permanent change, impairment, damage or disruption in his body function or structure, physical activity and/or quality of life).

^d For example intensive treatment in an emergency room or at home of allergic bronchospasm, blood dyscrasia or convulsions that do not result in hospitalisation or development of drug dependency or drug abuse.

The following adverse events must always be reported as an SAE using the important medical event criterion if no other seriousness criteria are applicable:

- Suspicion of transmission of infectious agents via the trial product

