12.1.6 Adverse event of special interest

An adverse event of special interest (AESI) is an event, which in the evaluation of safety, has a special focus. In this trial, the following AEs fulfil the AESI criteria:

- Thromboembolic events including but not limited to,
 - disseminated intravascular coagulation (DIC) (A),
 - clinical signs or laboratory indications of arterial and venous thrombosis including myocardial infarction (B),
 - pulmonary embolism (C),
 - stroke (D),
 - deep vein thrombosis (E),
 - other clinically significant thromboembolic events (F) and peripheral artery occlusion (see below G), see definitions below.

The AESIs must be reported on an AE form and a safety information form.

Protocol
 Trial ID:NN7415-4255
 UTN:U1111-1179-3872
 EudraCT no.:2016-000614-29

~~CONFIDENTIAL~~

Date:	05 May 2017	Novo Nordisk
Version:	2	
Status:	Final	
Page:	83 of 124	

A) Definition of disseminated intravascular coagulation (DIC), as defined below:

The definition of DIC in this trial should be made according to the International Society on Thrombosis and Haemostasis (ISTH) criteria. Thus, a DIC diagnosis may be based on clinical signs and symptoms of a bleeding tendency or thrombotic tendency, organ dysfunction and the laboratory parameters criteria as listed below:

- Platelet count ($>100 \times 10^9/L = 0$, $<100 \times 10^9/L = 1$, $<50 \times 10^9/L = 2$)
- Elevated D-dimer (no increase = 0, moderate increase = 2, strong increase = 3)
- Prolonged PT ($<3 \text{ s} = 0$, $>3 \text{ but } <6 \text{ s} = 1$, $>6 \text{ s} = 2$)
- Fibrinogen level ($>1 \text{ g/L} = 0$, $<1 \text{ g/L} = 1$)
- Calculate score: ≥ 5 compatible with overt DIC

(B) Myocardial infarction is defined according to the “Third Universal Definition of Myocardial Infarction”²⁴

Criteria for acute myocardial infarction - The term acute myocardial infarction (MI) should be used when there is evidence of myocardial necrosis in a clinical setting consistent with acute myocardial ischemia. Under these conditions any one of the following criteria meets the diagnosis for MI:

- Detection of a rise and/or fall of cardiac biomarker values [preferably cardiac troponin (cTn)] with at least one value above the 99th percentile upper reference limit (URL) and with at least one of the following:
 - Symptoms of ischemia.
 - New or presumed new significant ST-segment–T wave (ST–T) changes or new left bundle branch block (LBBB).
 - Development of pathological Q waves in the ECG.

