12.3 Follow-up of adverse events

The investigator must record follow-up information by updating the forms in the eCRF.

Follow-up information must be reported to Novo Nordisk according to the following:

- **SAEs:** All SAEs must be followed until the outcome of the event is “recovered/resolved”, “recovered/resolved with sequelae” or “fatal”, and until all queries have been resolved. Cases of chronic conditions, cancer or AEs ongoing at time of death (where death is due to another AE) may be closed with the outcome “recovering/resolving” or “not recovered/not resolved”. Cases can be closed with the outcome of “recovering/resolving” when the patient has completed the follow-up period and is expected by the investigator to recover.

The SAE follow-up information should only include new (e.g. corrections or additional) information and must be reported **within 24 hours** of the investigator’s first knowledge of the

Protocol
 Trial ID: NN7415-4255
 UTN: U1111-1179-3872
 EudraCT no.: 2016-000614-29

~~CONFIDENTIAL~~

Date:	05 May 2017	Novo Nordisk
Version:	2	
Status:	Final	
Page:	89 of 124	

information. This is also the case for previously non-serious AEs which subsequently become SAEs.

- **Non-serious AEs:** Non-serious AEs must be followed until the outcome of the event is “recovering/resolving”, “recovered/resolved” or “recovered/resolved with sequelae” or until the end of the follow-up period stated in the protocol, whichever comes first, and until all queries related to these AEs have been resolved. Cases of chronic conditions, cancer or AEs ongoing at time of death (where death is due to another AE) may be closed with the outcome “recovering/resolving” or “not recovered/not resolved”. Cases can be closed with the outcome of “recovering/resolving” when the patient has completed the follow-up period and is expected by the investigator to recover.
- **Non-serious AEs fulfilling the AESI criteria:** Non-serious AE fulfilling the AESI criteria must be followed as specified for non-serious AE. Follow-up information on AESIs should only include new (e.g. corrections or additional) information and must be reported **within 14 calendar days** of the investigator’s first knowledge of the information. This is also the case for previously reported non-serious AEs which subsequently fulfil the AESI criteria.

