12.7 Rules for putting enrolment on hold

If one of below mentioned criteria is fulfilled, enrolment of additional patients in the clinical trial program will be placed on hold. An urgent safety committee meeting will be scheduled to decide further actions. Dosing of patients on treatment may continue while further evaluation is made by the safety committee. A substantial amendment with relevant data must be submitted to the regulatory authorities to support restart of the trial.

- Significant thromboembolic event*
- Event of DIC
- Anaphylactic reaction related to trial drug administration
- Death of trial patient which may be related to the trial product
- Two or more other trial product related SAEs similar in nature have been reported and/or detected by laboratory measurements
- Trends in AEs, clinical observations or laboratory parameters which raise concerns about the safety of continued treatment

Protocol
 Trial ID:NN7415-4255
 UTN:U1111-1179-3872
 EudraCT no.:2016-000614-29

~~CONFIDENTIAL~~

Date:	05 May 2017	Novo Nordisk
Version:	2	
Status:	Final	
Page:	93 of 124	

* Superficial thrombophlebitis or venous thrombosis associated with indwelling catheters is not considered a significant thromboembolic event unless evaluated as such by the investigator

If two or more other trial product related SAEs similar in nature have been reported and/or detected by laboratory measurements, or if trends in AEs, clinical observations or laboratory parameters raise concerns about the safety of continued treatment, the safety committee (see section [12.8.1](#)) will then decide whether further dosing of any patients in the clinical trial program should be continued, paused or discontinued.

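### A thromboembolic event or DIC graded non-serious may be reported up to 14 days after first knowledge, although it can be a trigger for the enrolment hold and urgent safety meeting in section 12.7

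*Protocol*

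**What the plan says.** All references are to version 2 of the protocol.

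- **Section 12.1.6** introduces its list with "In this trial, the following AEs fulfil the AESI criteria". The list has one class, "Thromboembolic events including but not limited to", whose first item is "disseminated intravascular coagulation (DIC) (A".
- **Section 12.2** gives two timelines. For SAEs: "The AE form within 24 hours and the safety information form within 5 calendar days of the investigator's first knowledge of the SAE". For the rest of the AESI class: "Non-serious AEs fulfilling the AESI criteria: The AE form and safety information form within 14 calendar days".
- **Section 12.3** carries the second timeline into follow-up: "Non-serious AE fulfilling the AESI criteria must be followed as specified for non-serious AE". New information on these events has 14 calendar days. So does an already reported non-serious event that later turns out to be an AESI.
- **Section 12.1.2** names events that are SAEs by rule: "The following adverse events must always be reported as an SAE using the important medical event criterion if no other seriousness criteria are applicable". The two entries are suspected transmission of an infectious agent through the product and Hy's law liver injury. Thromboembolic events and DIC are not there.
- **Section 12.7** lists a significant thromboembolic event and an event of DIC among the criteria for holding enrolment across the clinical programme. Neither carries a seriousness condition. Once a criterion is met: "An urgent safety committee meeting will be scheduled to decide further actions". A footnote takes superficial thrombophlebitis and catheter-related venous thrombosis out of the significant category, unless the investigator judges otherwise. Dosing of patients already on treatment may go on while the committee evaluates.

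**The concern.** A hold rule works no faster than the reporting rule that feeds it. Section 12.7 treats these events as urgent at any level of seriousness, but 12.2 ties speed of reporting to seriousness alone. A site can therefore know of an event that meets a hold criterion, grade it non-serious, and comply with 12.2 by notifying the sponsor two weeks later.

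Thrombosis is the principal potential risk named in section 18.1, and the hold is meant to protect the next patient to be enrolled. The same section says that marked fibrinogen, D-dimer and F1+2 changes in the preceding multiple-dose trial were not judged clinically significant by the investigators. Grading of coagulation findings at site level is thus a realistic place for differences in judgement.

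**Working it through.** There is no figure in the protocol to reproduce. The check is a comparison of sections, followed by a simple accrual illustration.

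**Step 1. Can an event meet 12.7 and stay off the 24-hour route?**

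| Question | Section | Answer |
|---|---|---|
| Does the hold depend on seriousness? | 12.7 | No, for a significant thromboembolic event or DIC |
| Are these events SAEs by rule? | 12.1.2 | No, they are not on the always-SAE list |
| Can they be SAEs by judgement? | 12.1.2 | Yes, through the important-medical-event criterion, which is worded permissively |
| What applies if they are graded non-serious? | 12.2, 12.3 | 14 calendar days, for the first report and for updates |

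The laboratory part of the DIC definition in 12.1.6 can reach its threshold of 5 on laboratory values alone: strong D-dimer increase (3) + fibrinogen below 1 g/L (1) + platelets below 100 × 10⁹/L (1) = 5. Section 12.1.6 allows deep vein thrombosis to be shown by ultrasound, which need not involve admission. Section 12.2 itself provides for AESIs that are not serious.

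**Step 2. Does another route set a deadline?**

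- Section 8.1.4: stopping trial product needs an IWRS session and an end-of-treatment form. No time limit is given for either.
- Section 13.2: eCRF entry is preferred within 5 days of the visit, which is not a requirement.
- Sections 8.5 and 12.8.1: fibrinogen and D-dimer are measured centrally (platelets locally), and the safety committee carries out ongoing surveillance. Neither section sets an alert time.

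These routes may bring the event to light sooner, but none obliges anyone to report it sooner. Figure 12-1 and the DMC charter are not visible in the text at hand.

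**Step 3. Size during recruitment.**

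Inputs:
- 33 patients planned to start trial product (section 6.1).
- First visits planned from 16 Aug to 16 Dec 2017 (section 7), which is 122 days.

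Expected new starts in a window of *w* days, under even accrual = 33/122 × *w*, where 33/122 = 0.270 per day.

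- *w* = 14: 0.270 × 14 = 3.8 patients.
- *w* = 1: 0.270 × 1 = 0.27, about 0.3 patients.
- Difference: 0.270 × 13 = 3.5 patients.

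Only this trial is counted, although the hold covers the programme.

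**Step 4. How much treated time the illustration covers.**

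Each patient is treated for 76 × 7 = 532 days. Under even accrual, and ignoring the screening lag and dropout, the average treated time inside the 122-day window is 122/2 = 61 days. That is 61/532, about 11% of planned exposure. Over the remaining time no further patient in this trial can be started, so the extra starts are zero.

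**The case against.** The strongest reply is that the important-medical-event criterion already covers the obvious examples. Section 12.1.2 makes an event a potential SAE without admission if it may jeopardise the patient and may need intervention to prevent a serious outcome. Its footnote mentions intensive treatment of blood dyscrasia in an emergency room or at home. An outpatient deep vein thrombosis or overt DIC would often qualify and go by the 24-hour route. This stands as a limit on frequency. It does not close the gap, because the criterion leaves the decision to judgement while the hold criteria do not depend on that grading.

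Three stronger readings are tempting, and the protocol does not support them:

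- **That every AESI is a hold event.** The AESI class is wider. It takes in clinical signs or laboratory indications of thrombosis, and it is open-ended. Section 12.7 needs a significant event or DIC and sets superficial and catheter-related thrombosis aside. A 14-day timeline for that remainder is reasonable.
- **That the delay gives each treated patient up to 14 doses that the hold would have prevented.** Section 12.7 stops enrolment and lets dosing continue pending evaluation. Late reporting postpones the committee's decision; it does not by itself cause those doses. For the affected patient, section 6.4 requires discontinuation after a thromboembolic event or DIC, whatever the reporting time.
- **That adding all thromboembolic events to the always-SAE list is an equivalent remedy.** It would change seriousness coding in the adverse event summaries, feed into SUSAR assessment, and sweep in superficial events that the protocol treats as not significant.

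**Conclusion.** The gap is real but narrow. Sections 12.2 and 12.3 permit up to 14 calendar days from first knowledge to report or update an event that section 12.7 treats as urgent, if the investigator grades it non-serious. No other section sets a shorter limit for such an event.

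The figure of about 3.8 further starts, against about 0.3 with a 24-hour rule, is a conditional worst case. It requires that the event falls within recruitment, that it is graded non-serious, that the report comes on the last permitted day, and that accrual is even. It is not an expected number for the trial. Once recruitment has closed, the consequence is a later safety committee review and no additional starts in this trial.

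A reader might infer that 12.7 demands an immediate halt, or that a report on day 14 is late. The section speaks of a hold and an urgent meeting without fixing a time, and a day-14 report would be on time. The fault is that the permitted time does not fit the purpose of the hold.

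**What to change.** In sections 12.2 and 12.3 and in Figure 12-1, add that any event meeting a section 12.7 hold criterion, regardless of seriousness, is reported on the AE form within 24 hours of the investigator's first knowledge, and on the safety information form within 5 calendar days. State that this includes an event first reported as a non-serious AE that later meets a criterion, with the clock running from knowledge that it does. Add a cross-reference in 12.7 so that the hold rule names the reporting rule it relies on.

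Keep the 14-day timeline for the remaining non-serious AESIs, and leave the always-SAE list in 12.1.2 as it is.

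The cost is a few lines of wording, a change to one figure and a note in site training. Sites already operate the 24-hour SAE route. The downside is slightly more urgent paperwork for a few events, some of which may later be judged minor.

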12.3 Follow-up of adverse events

The investigator must record follow-up information by updating the forms in the eCRF.

Follow-up information must be reported to Novo Nordisk according to the following:

- **SAEs:** All SAEs must be followed until the outcome of the event is “recovered/resolved”, “recovered/resolved with sequelae” or “fatal”, and until all queries have been resolved. Cases of chronic conditions, cancer or AEs ongoing at time of death (where death is due to another AE) may be closed with the outcome “recovering/resolving” or “not recovered/not resolved”. Cases can be closed with the outcome of “recovering/resolving” when the patient has completed the follow-up period and is expected by the investigator to recover.

The SAE follow-up information should only include new (e.g. corrections or additional) information and must be reported **within 24 hours** of the investigator’s first knowledge of the

Protocol
 Trial ID: NN7415-4255
 UTN: U1111-1179-3872
 EudraCT no.: 2016-000614-29

~~CONFIDENTIAL~~

Date:	05 May 2017	Novo Nordisk
Version:	2	
Status:	Final	
Page:	89 of 124	

information. This is also the case for previously non-serious AEs which subsequently become SAEs.

- **Non-serious AEs:** Non-serious AEs must be followed until the outcome of the event is “recovering/resolving”, “recovered/resolved” or “recovered/resolved with sequelae” or until the end of the follow-up period stated in the protocol, whichever comes first, and until all queries related to these AEs have been resolved. Cases of chronic conditions, cancer or AEs ongoing at time of death (where death is due to another AE) may be closed with the outcome “recovering/resolving” or “not recovered/not resolved”. Cases can be closed with the outcome of “recovering/resolving” when the patient has completed the follow-up period and is expected by the investigator to recover.
- **Non-serious AEs fulfilling the AESI criteria:** Non-serious AE fulfilling the AESI criteria must be followed as specified for non-serious AE. Follow-up information on AESIs should only include new (e.g. corrections or additional) information and must be reported **within 14 calendar days** of the investigator’s first knowledge of the information. This is also the case for previously reported non-serious AEs which subsequently fulfil the AESI criteria.

The investigator must ensure that the recording of the worst case severity and seriousness of an event is kept throughout the trial. A worsening of an unresolved AE must be reported as follow up with re-assessment of severity and/or seriousness of the event.

Queries or follow-up requests from Novo Nordisk must be responded to **within 14 calendar days** from the date of receipt of the request, unless otherwise specified in the follow-up request.

SAEs after end of trial: If the investigator becomes aware of an SAE with a suspected causal relationship to the investigational medicinal product occurring to a patient after the patient has ended the trial, the investigator should report this SAE within the same timelines as for SAEs during the trial.

